8.2 Response and Evaluation Endpoints

Response and progression will be evaluated in this study using the revised international criteria (1.1) proposed by the RECIST (Response Evaluation Criteria in Solid Tumours) committee as well as the Immune-Related modified RECIST. Investigators should continue treatment, as appropriate, in the absence of unacceptable toxicity, until unequivocal disease progression. This is particularly important for patients in whom pseudoprogression may have occurred. Follow up response assessments must be continued until unequivocal disease progression has occurred.

8.2.1 Measurable Disease

Measurable *tumour lesions* are defined as those that can be accurately measured in at least one dimension (longest diameter to be recorded) as ≥ 20 mm with chest x-ray and as ≥ 10 mm with CT scan or clinical examination. Bone lesions are considered measurable only if assessed by CT scan and have an identifiable soft tissue component that meets these requirements (soft tissue component ≥ 10 mm by CT scan). *Malignant lymph nodes* must be ≥ 15 mm in the short axis to be considered measurable; only the short axis will be measured and followed. All tumour measurements must be recorded in millimetres (or decimal fractions of centimetres). Previously irradiated lesions are not considered measurable unless progression has been documented in the lesion.

8.2.2 Non-measurable Disease

All other lesions (or sites of disease), including small lesions are considered non-measurable disease. Bone lesions without a measurable soft tissue component, leptomeningeal disease, ascites, pleural/pericardial effusions, lymphangitis cutis/pulmonis, inflammatory breast disease, lymphangitic involvement of lung or skin and abdominal masses followed by clinical examination are all non-measurable. Lesions in previously irradiated areas are non-measurable, unless progression has been demonstrated.

8.2.3 Target Lesions

When more than one measurable tumour lesion is present at baseline all lesions up to *a maximum of 5 lesions total* (and a maximum of *2 lesions per organ*) representative of all involved organs should be identified as target lesions and will be recorded and measured at baseline. Target lesions should be selected on the basis of their size (lesions with the longest diameter), be representative of all involved organs, but in addition should be those that lend themselves to *reproducible repeated measurements*. Note that pathological nodes must meet the criterion of a short axis of ≥ 15 mm by CT scan and only the *short* axis of these nodes will contribute to the baseline sum. All other pathological nodes (those with short axis ≥ 10 mm but < 15 mm) should be considered non-target lesions. Nodes that have a short axis < 10 mm are considered non- pathological and should not be recorded or followed (see 8.2.4). At baseline, the sum of the target lesions (longest diameter of tumour lesions plus short axis of lymph nodes: overall maximum of 5) is to be recorded.

After baseline, a value should be provided on the CRF for all identified target lesions for each assessment, even if very small. If extremely small and faint lesions cannot be accurately measured but are deemed to be present, a default value of 5 mm may be used. If lesions are too small to measure and indeed are believed to be absent, a default value of 0 mm may be used.

8.2.4 Non-target Lesions

All non-measurable lesions (or sites of disease) plus any measurable lesions over and above those listed as target lesions are considered *non-target lesions*. Measurements are not required but these lesions should be noted at baseline and should be followed as “present” or “absent”.

8.2.5 Response

All patients will have their BEST RESPONSE from the start of study treatment until the end of treatment classified as outlined below:

Complete Response (CR): disappearance of *target* and *non-target* lesions and normalization of tumour markers. Pathological lymph nodes must have short axis measures < 10 mm (Note: continue to record the measurement even if < 10 mm and considered CR). Residual lesions (other than nodes < 10 mm) thought to be non-malignant should be further investigated (by cytology specialized imaging or other techniques as appropriate for individual cases [*Eisenhauer 2009*]) before CR can be accepted. Confirmation of response is required.

Partial Response (PR): at least a 30% decrease in the sum of measures (longest diameter for tumour lesions and short axis measure for nodes) of target lesions, taking as reference the baseline sum of diameters. Non target lesions must be non-PD. Confirmation of response is required.

Stable Disease (SD): Neither sufficient shrinkage to qualify for PR nor sufficient increase to qualify for PD taking as reference the smallest sum of diameters on study.

Progressive Disease (PD): at least a 20% increase in the sum of diameters of measured lesions taking as references the smallest sum of diameters recorded on study (including baseline) AND an absolute increase of ≥ 5 mm. Appearance of new lesions will also constitute progressive disease (including lesions in previously unassessed areas). In exceptional circumstances, unequivocal progression of non-target disease may be accepted as evidence of disease progression, where the overall tumour burden appears to have increased by at least 73% in volume or, in select instances where tumour burden has increased sufficiently to require urgent medical intervention (e.g. radiation for spinal cord compression or drainage of a fluid collection). Modest increases in the size of one or more non-target lesions are NOT considered unequivocal progression. If the evidence of PD is equivocal (target or non-target), treatment may continue until the next assessment, but if confirmed, the earlier date must be used.

Table 1: Integration of Target, non-Target and New Lesions into Response Assessment:

Target Lesions	Non-Target Lesions	New Lesions	Overall Response	Best Response for this Category also Requires
Target lesions ± non target lesions				
CR	CR	No	CR	Normalization of tumour markers, tumour nodes < 10 mm
CR	Non-CR/Non-PD	No	PR	
CR	Not all evaluated	No	PR	
PR	Non-PD/ not all evaluated	No	PR	
SD	Non-PD/ not all evaluated	No	SD	Documented at least once ≥ 4 wks. from baseline*
Not all evaluated	Non-PD	No	NE	
PD	Any	Any	PD	
Any	PD	Any	PD	
Any	Any	Yes**	PD	
Non target lesions ONLY				
No Target	CR	No	CR	Normalization of tumour markers, tumour nodes < 10 mm
No Target	Non-CR/non-PD	No	Non-CR/non-PD	
No Target	Not all evaluated	No	NE	
No Target	Unequivocal PD	Any	PD	
No Target	Any	Yes	PD	

Note: Patients with a global deterioration of health status requiring discontinuation of treatment without objective evidence of disease progression at that time should be reported as “symptomatic deterioration”. This is a reason for stopping therapy, but is NOT objective PD. Every effort should be made to document the objective progression even after discontinuation of treatment.
 
* For this study, baseline is defined as the date of enrollment.
 
** Investigators should record all new lesions; if the new lesion is felt to be equivocal, treatment may be continued pending further assessments – see Table 2.
				

For non randomized trials, where confirmation of response is required, best overall response can be interpreted as follows:

Response: First Time Point	Subsequent Time Point	BEST Overall Response	Also Requires
CR	CR	CR	Normalization of tumour markers, tumour nodes < 10 mm
CR	PR	SD, PD or PR (see comment*)	
CR	SD	SD provided minimum criteria for SD duration met, otherwise, PD	
CR	PD	SD provided minimum criteria for SD duration met, otherwise, PD	
CR	NE	SD provided minimum criteria for SD duration met, otherwise NE	
PR	CR	PR	
PR	PR	PR	
PR	SD	SD	
PR	PD	SD provided minimum criteria for SD duration met, otherwise, PD	
PR	NE	SD provided minimum criteria for SD duration met, otherwise NE	
NE	NE	NE	
* may consider PR providing initial “CR” likely PR on subsequent review – then original CR should be corrected. Recurrence of lesion after true CR is PD.			

8.3 Immune-Related Response Assessment

Overall response will also be assessed using iRECIST [Seymour 2017]. Immunotherapeutics may result in infiltration of immune cells leading to transient increase in the size in malignant lesions, or undetectable lesions becoming detectable. The criteria are identical to those of RECIST 1.1 in many respects but have been adapted to account for instances where an increase in tumour burden, or the appearance of new lesions, does not reflect true tumour progression.

Key differences are described below. All responses defined using iRECIST criteria are designated with a prefix. iRECIST time-point and best overall responses will be recorded separately.

Confirming Progression

Unlike RECIST 1.1, iRECIST requires the confirmation of progression and uses the terms iUPD (unconfirmed progression) and iCPD (confirmed progression). Confirmatory scans should be performed at least 4 weeks, but no longer than 8 weeks after iUPD.

iCPD is confirmed if further increase in tumour burden, compared to the last assessment, is seen as evidenced by one or more of the following:

- Continued increase in tumour burden (from iUPD) where RECIST 1.1 definitions of progression had been met (from nadir) in target, non-target disease or new lesions - Progression in target disease worsens with an increase of at least 5 mm in the absolute value of the sum:

- Continued unequivocal progression in non-target disease with an increase in tumour burden;
- Increase in size of previously identified new lesion (s) (an increase of at least 5 mm in the absolute value of the sum of those considered to be target new lesions) or additional new lesions.
- RECIST 1.1 criteria are met in lesions types (target or non-target or new lesions) where progression was not previously identified, including the appearance of additional new lesions.

If iUPD is not confirmed at the next assessment, then the appropriate response will be assigned (iUPD if the criteria are still met, but no worsening, or iSD, iPR or iCR if those criteria are met compared to baseline). As can be seen in table 2, the prior documentation of iUPD does not preclude assigning iCR, iPR, or iSD in subsequent time-point assessments or as best overall response (BOR) providing that iCPD is not documented at the next assessment after iUPD.

New Lesions

New lesions should be assessed and measured as they appear using RECIST 1.1 criteria (maximum of 5 lesions, no more than 2 per site, at least 10 mm in long axis (or 15 mm in short axis for nodal lesions), and recorded as New Lesions-Target (NLT) and New Lesion-Non-Target (NLNT) to allow clear differentiation from baseline target and non-target lesions.

New lesions may either meet the criteria of NLT or NLNT to drive iUPD (or iCPD). However, the measurements of NLT should NOT be included in the sum of measures of original target lesions identified at baseline. Rather, these measurements will be collected on a separate table in the case record form.

PD is confirmed in the New Lesion category if the next imaging assessment, conducted at least 4 weeks (but not more than 8 weeks) after iUPD confirms further progression from iUPD with either an increase of at least 5 mm in the absolute value of the sum of NLT OR an increase (but not necessarily unequivocal increase) in the size of NLNT lesions OR the appearance of additional new lesions.

Table 2: Time-point (TP) iResponse

Target Lesions*	Non-Target Lesions*	New Lesions*	Time Point Response	
			No prior iUPD**	Prior iUPD**, ***
iCR	iCR	No	iCR	iCR
iCR	Non-iCR/Non-iUPD	No	iPR	iPR
iPR	Non-iCR/Non-iUPD	No	iPR	iPR
iSD	Non-iCR/Non-iUPD	No	iSD	iSD
iUPD with no change OR decrease from last TP	iUPD with no change OR decrease from last TP	Yes	NA	NLs confirms iCPD if NLs were previously identified and increase in size (≥ 5 mm in SOM for NLT or any increase for NLNT) or number. If no change in NLs (size or number) from last TP, remains iUPD
iSD	iUPD	No	iUPD	Remains iUPD unless iCPD confirmed based in further increase in size of NT disease (need not meet RECIST 1.1 criteria for unequivocal PD)
iUPD	Non-iCR/Non-iUPD	No	iUPD	Remains iUPD unless iCPD confirmed based on: - further increase in SOM of at least 5 mm, otherwise remains iUPD
iUPD	iUPD	No	iUPD	Remains iUPD unless iCPD confirmed based on further increase in: - previously identified T lesion iUPD SOM ≥ 5 mm and / or - NT lesion iUPD (prior assessment - need not be unequivocal PD)
iUPD	iUPD	Yes	iUPD	Remains iUPD unless iCPD confirmed based on further increase in: - previously identified T lesion iUPD ≥ 5 mm and / or - previously identified NT lesion iUPD (need not be unequivocal) and /or - size or number of new lesions previously identified
Non-iUPD/PD	Non-iUPD/PD	Yes	iUPD	Remains iUPD unless iCPD confirmed based on - increase in size or number of new lesions previously identified

* Using RECIST 1.1 principles. If no PSPD occurs, RECIST 1.1 and iRECIST categories for CR, PR and SD would be the same.
 ** In any lesion category.
 *** Previously identified in assessment immediately prior to this TP.

Table 3: iRECIST Best Overall Response (iBOR)

All patients will have their iBOR from the start of study treatment until the end of treatment classified as outlined below.

TPR1	TPR2	TPR3	TPR4	TPR5	iBOR
iCR	iCR, iPR, iUPD, NE	iCR, iPR, iUPD, NE	iUPD	iCPD	iCR
iUPD	iPR, iSD, NE	iCR	iCR, iPR, iSD, iUPD, NE	iCR, iPR, iSD, iUPD, iCPD, NE	iCR
iUPD	iPR	iPR, iSD, iUPD, NE	iPR, iSD, iUPD, NE, iCPD	iPR, iSD, iUPD, NE, iCPD	iPR
iUPD	iSD, NE	PR	iPR, iSD, iUPD, NE	iPR, iSD, iUPD, iCPD, NE	iPR
iUPD	iSD	iSD, iUPD, NE	iSD, iUPD, iCPD, NE	iSD, iUPD, ICPD, NE	iSD
iUPD	iCPD	Anything	Anything	Anything	iCPD
iUPD	iUPD	iCPD	Anything	Anything	iCPD
iUPD	NE	NE	NE	NE	iUPD

- Table assumes a randomized study where confirmation of CR or PR is not required.
- NE = not evaluable that cycle.
- Designation “I” for BOR can be used to indicate prior iUPD to aid in data interpretation.
- For patients with non-target disease only at baseline, only CR or non-CR/non-PD can be assigned at each TPR but is not shown in the table for ease of presentation.

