1.2 Secondary Objectives

- To evaluate Disease Control Rate (DCR, defined as CR or PR or stable disease (SD) > 16 weeks in duration) of CFI-400945 given with durvalumab.
- To evaluate the immune-related response rate (iRECIST) of CFI-400945 given with durvalumab.
- To establish the safety and tolerability of CFI-400945 given orally in combination with durvalumab in a q4w schedule and to confirm the recommended phase II dose (RP2D) in patients with metastatic triple negative breast cancer (TNBC).

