13.0 STATISTICAL CONSIDERATIONS

This is an open label multicentre phase II trial to evaluate the anti-tumour activity of CFI-400945 when given with durvalumab by determining the objective response rate in patients as defined in Section 4.1.1. A 2-stage Simon minimax design will be used.

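### The iRECIST best-response table assumes a randomized trial without response confirmation, so in this single-arm trial the secondary iRECIST response rate may count unconfirmed responses

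*Combined protocol and SAP*

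**What the plan says.** **Objective.** Section 1.2 lists as a secondary objective: "To evaluate the immune-related response rate (iRECIST) of CFI-400945 given with durvalumab". Section 13.1 names this rate but does not say whether it counts confirmed responses. It gives no test or threshold for it.

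**Design.** One treatment, no randomization. Section 13.0: "A 2-stage Simon minimax design will be used".

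**RECIST 1.1.** Section 8.2.5 requires confirmation for CR and for PR; the PR definition ends "Non target lesions must be non-PD. Confirmation of response is required". Best response is then read from a table introduced with "For non randomized trials, where confirmation of response is required, best overall response can be interpreted as follows".

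**iRECIST.** Section 8.3 introduces Table 3 with "All patients will have their iBOR from the start of study treatment until the end of treatment classified as outlined below". The first note under the table is "Table assumes a randomized study where confirmation of CR or PR is not required". The note under Table 2 says "If no PSPD occurs, RECIST 1.1 and iRECIST categories for CR, PR and SD would be the same".

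**Scans.** Footnote 14 to the Section 5.0 flowsheet asks for repeat imaging between 4 and 8 weeks later to confirm response, and names iCR and iPR as well as CR and PR. Section 8.1.2 tells investigators that the two criteria differ in their confirmatory scans, without saying how.

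**The concern.** For the same patients, the protocol uses the non-randomized best-response rule for RECIST and the randomized one for iRECIST, and gives no reason. Section 8.3 sets out to describe the key differences between the two systems. The differences it describes are confirmation of progression and handling of new lesions; a waiver of response confirmation is not among them.

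The iRECIST rate will naturally be read beside the primary objective response rate (ORR). If it is higher, readers will credit responses after pseudoprogression, which iRECIST is meant to capture. Under the Table 3 note, the excess could also contain responses seen on one scan only, and the two sources could not be separated. Two analysts following different parts of the protocol could also derive different rates from the same data.

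**Working it through.** **1. The plan's own figures.** None is given for the iRECIST rate. Section 13.2 gives the primary design: 15 patients, stop at 2 or fewer responses, 28 in total, reject at 8 or more, with 5% type I error and power 0.8 at a true rate of 35%.

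Probability of rejection = sum over x = 3 to 15 of P(Bin(15, p) = x) × P(Bin(13, p) ≥ 8 − x).

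- p = 0.15: 0.0461, within the stated 5%.
- p = 0.35: 0.8027, matching the stated 0.8.

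The design reproduces. It uses RECIST 1.1 responses only, so nothing below changes it.

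**2. Does Table 3 credit a single response scan?** All its rows start with iCR or iUPD. Each of the four response rows accepts a sequence with one response scan. In these sequences iCPD appears only directly after iUPD, as Table 2 requires.

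| Table 3 row | Permitted sequence | iBOR |
|---|---|---|
| 1 | iCR, NE, NE, iUPD, iCPD | iCR |
| 2 | iUPD, iSD, iCR, iUPD, iCPD | iCR |
| 3 | iUPD, iPR, iSD, iSD, iSD | iPR |
| 4 | iUPD, iSD, iPR (printed as PR), iSD, iSD | iPR |

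Row 1 compares directly with Section 8.2.5, where CR followed by NE is SD if the minimum SD duration is met, and NE if not. Row 3 can only be compared by analogy with PR followed by SD, which Section 8.2.5 scores as SD, because the RECIST table has no row starting with progression. These are permitted table entries, not patient frequencies.

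**3. Patients starting with iPR or iSD.** Table 3 has no row for them. Its note waives confirmation. The Table 2 note equates the RECIST and iRECIST categories when there is no pseudoprogression; at best-response level that cannot hold if only one system requires confirmation. Footnote 14 also points to confirmation. Nothing decides between these.

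**4. Direction.** Every patient with a confirmed iRECIST response has at least one iCR or iPR scan. Confirmed responders are therefore a subset of those counted when confirmation is waived. With the same denominator, the rate under the waiver is equal or higher.

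**5. Size.** With n evaluable patients and k credited on one response scan only, the excess is k/n.

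- n = 28: 1/28 = 3.6 percentage points each.
- n = 15 (stop after stage 1): 1/15 = 6.7 points each.

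The documents do not give k. Assumed illustrations, with the exact 95% interval that Section 13.1 specifies for the ORR:

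| n | k = 0 | k = 1 | k = 2 |
|---|---|---|---|
| 28 | 5/28 = 17.9% (6.1 to 36.9) | 6/28 = 21.4% (8.3 to 41.0) | 7/28 = 25.0% (10.7 to 44.9) |
| 15 | 2/15 = 13.3% (1.7 to 40.5) | 3/15 = 20.0% (4.3 to 48.1) | not computed |

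The first interval in each row is 36.9 − 6.1 = 30.8 and 40.5 − 1.7 = 38.8 points wide, so one patient's effect is small beside the sampling uncertainty.

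**The case against.** The best counter-argument is that confirmation was meant to carry over to iRECIST, and that the note only discloses what the table does not display. Section 8.3 says the two systems agree in many respects, and waived response confirmation is not among the differences it describes. Footnote 14 asks for confirmatory scans for iCR and iPR. In the flowsheet its superscript appears only on the post-treatment imaging columns, but the same sentence covers iUPD, and its 4-to-8-week interval matches the iUPD rule in Section 8.3. Because both best-response windows close at the end of treatment, a purely post-treatment confirmation would do little.

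Much of this stands. It shows that a confirmed iRECIST rate is a reasonable reading, and that for patients starting with iPR or iSD the fault is a conflict rather than a clear waiver. It does not remove the point. No sentence feeds footnote 14 into the iBOR, Section 13.1 is silent, and the rows Table 3 does contain give a response on one scan.

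A reader might infer more than the documents support in three ways:

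- **That Table 3 settles every patient's iBOR without confirmation.** It has no rows starting with iPR or iSD, so its explicit single-scan credit covers only patients starting with iCR or iUPD.
- **That a response after iUPD is itself the fault.** Section 8.3 intends to allow it. The issue is only that the response need not be seen again.
- **That the iUPD-first rows contradict the RECIST table directly.** That table has no progression-first row. If the first progression stands, the RECIST result is PD, so the comparison is an analogy.

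**Conclusion.** The point holds as a conflict within the protocol affecting one secondary, descriptive endpoint. Table 3 and its note carry an assumption that does not fit this trial. Followed as written, they can only leave the iRECIST rate equal to or above a confirmed rate, by 3.6 points per affected patient at n = 28 or 6.7 at n = 15. This assumes the same evaluable denominator for both rates, which the plan does not state separately for iRECIST.

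It would be wrong to conclude that the rate will be inflated: the number of affected patients is unknown and may be zero. It would also be wrong to carry the point over to the primary analysis. The ORR uses confirmed RECIST 1.1 responses, and the stopping rule, type I error and power are unaffected. The plan sets no formal comparison between the two rates. The correction should be made because it is cheap and because, without it, any excess over the ORR could not be attributed to responses after pseudoprogression.

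**What to change.** - **Section 8.3, Table 3 note.** Replace it with a statement that, because the trial is not randomized, iCR and iPR (including after iUPD) must be confirmed at a subsequent time point under the rule Section 8.2.5 uses for RECIST. An unconfirmed response becomes iSD if the minimum SD duration is met, and otherwise NE, iUPD or iCPD as applicable.
- **Table 3 rows.** Adjust the response rows to match, and add rows for sequences starting with iPR and with iSD.
- **Footnote 14.** Reconcile it with the revised table, so that the protocol states one confirmation rule and shows which scans it applies to.
- **Section 13.1.** State that the iRECIST response rate is the confirmed rate. Report any unconfirmed rate separately and label it as such.
- **Leave the RECIST best-response rules unchanged**, since they define the primary endpoint.

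The cost is one table with its note, a footnote reconciliation and a short addition to Section 13.1. No new on-treatment scans are needed, because the 8-weekly imaging already supplies the subsequent time point. A response first seen on the last on-treatment scan would be handled as for RECIST, since both best-response windows run to the end of treatment. The downside is a possibly lower iRECIST rate.
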